## 7.3 STUDY SCHEDULE

### 7.3.1 SCREENING

A trained research assistant will screen prospective participants who call in for the study according to the inclusion/exclusion criteria. Research assistants will also provide an explanation of the study timeline and schedule of assessments, and compensation during this call, and answer any questions that participants may have about participation. If any subject is questionable for inclusion, [name] (a licensed clinical psychologist) and [name] (a licensed M.D.), will make the final determination of eligibility. If a patient is deemed eligible for participation and wishes to proceed, an appointment will be made for a Baseline remote session. All female potential study participants of child-bearing age will then be asked to participate in pregnancy testing to verify eligibility. A trained research assistant will deliver a urine receptacle to the participant's home. The participant will then use the restroom in their home and return the receptacle to the research assistant to complete the urine test in the mobile laboratory.

### 7.3.2 ENROLLMENT/BASELINE

Potential participants who meet inclusion criteria will be scheduled for a baseline session. A trained research assistant will meet remotely with the participant via phone or Zoom. Each participant will go through the informed consent process. Once consented, participants will complete current and historical health and substance use assessments and cognitive testing (see Table 7.1). Participants will complete assessments via emailed, individually tailored links hosted by and integrated into the study's REDCap databases (<https://redcap.ucdenver.edu/>). Participants will then receive a consultation from research staff on the range of edible *Cannabis* products and basic information about their various cannabinoid profiles, approximate prices, and nearby locations where participants may choose to purchase their product. Again, research staff will not advise study participants to purchase any specific product. Participants will be compensated with a \$60 grocery store gift card for their time and effort at the end of the visit, which will be mailed to their home.

### 7.3.3 FOLLOW-UP

Figure 3. Example of an edible *Cannabis* product

Colorado requires all orally administered *Cannabis* products to be tested by a state lab, which allows us to have a precise measure of potency despite the inability to assign products to users. While participants are not blind to the type of product they are ingesting, it is important to note that the subjective effects of THC and CBD are quite different, and thus participants who are not naïve to *Cannabis* use would likely not be blind even if assigned to a product. Importantly, the researchers who conduct the assessments as well as most of the senior investigators *will* be blind to condition. The observational aspect of the design involves the instruction to use their selected product at home consistent with the packaging directions and/or as they see fit. Consistent with federal law, study staff will not provide any directions regarding dosing and administration. For verification purposes, participants will take and send a picture of their purchased product to the CUChange Lab via the REDCap system as mentioned in section 6.1.3.

**Pre- and Post- Administration Assessment (Ta1-Tc1).** The Pre- and Post- Administration Assessment will take place two weeks (+/- 4 days) following the baseline session. A trained research assistant will meet remotely with the participant via phone or Zoom. Links to assessments will be emailed to the participant at the start of the session. Prior to taking their *Cannabis*, participants will complete self-report assessments, including those assessing quantity/frequency of *Cannabis* use and symptom severity over the prior two weeks (Ta1). They will then consume their orally administered *Cannabis*. Because 60 minutes is the average time that CBD and THC levels begin to peak in the blood after oral administration of *Cannabis* extract, assessments of the acute effects of *Cannabis* (see Table 7.2) will begin one hour (+/- 5 minutes) post-edible consumption (Tb1). After peak, levels steadily decrease over the next 2-3 hours and by 4 hours post-ingestion begin to rapidly drop off in blood. To account for individual differences in metabolism and sensitivity, participants will be assessed again at 2 hours (+/- 5 minutes) post-consumption (Tc1). After completing the 1- and 2- hour post-consumption assessments, participants will receive a \$100 grocery store gift card as compensation for their time and effort, which will be mailed to their home.

#### 7.3.4 FINAL STUDY VISIT

***Ad Libitum Cannabis Administration at Home.*** The participant will use their orally administered *Cannabis ad libitum* at home. This aspect of the design differentiates the proposed research from a classical interventional clinical trial, which is critically important because it is the only path forward for research on orally administered, legal market *Cannabis* given current federal law. It is well known in the pain and broader medication literatures that expectancies regarding the effects of a medication have profound influences on the patient experience of symptom reduction.

At the end of the Pre- and Post- Administration Assessment, participants may elect to continue use of the same product, switch to another product, or discontinue their *Cannabis* use. While the main observational portion of the study will be complete at that point, we will follow-up with participants in regard to their symptoms levels, *Cannabis* use, and cognition, using an online survey one month (+/- 7 days) later (M1), in keeping with the observational nature of the design. This aspect will provide important data on feasibility of longer-term follow-up with this population, and further valuable data in regard to patient choice, patient behavior, patterns of use of *Cannabis* products, and associated experience of symptoms related to cancer treatment in a fully-powered iteration of the study. The survey will assess their *Cannabis* use, other substance use, symptom levels (pain, anxiety, and sleep), quality of life, and subjective and objective cognitive functioning over the past month. We also will conduct the final health status and treatment regimen review of the participant's EMR separately at this time point via Health Data Compass. Participants will receive a \$10 grocery store card as compensation for their time and effort, which will be mailed to their home.

### **7.3.5 Schedule of Events Table**

**Table 7.3 Schedule of Events**

		Demographics	AEs	MCQ	AUDIT	TLFB	EMR Review	Obj. Cognition	Sub. Cognition	FACT-G	PSQI	Anx-Mood (State)	Anx-Mood (Trait)	Pain (7 days)	Pain (Right now)
T00: Baseline	X	X*	X	X	X	X	X	X	X	X	X	X	X	X	
Ta1: 2-Week Pre-Acute Use		X	X		X			X	X	X	X	X	X	X	X
Tb1: 2-Week 1-Hour Post-Acute Use		X	X					X				X			X
Tc1: 2-Week 2-Hour Post-Acute Use		X	X					X				X			X
M1: 1-Month Follow-Up		X	X	X	X	X	X	X	X	X	X	X	X	X	
	
MCQ = Marijuana Craving Questionnaire      AUDIT = Alcohol Use Disorder Identification Test      TLFB = Timeline Followback Substance Use Assessment  Objective Cognition = Stroop task, Shape/Color Shifting Task.  Subjective Cognition = Functional Assessment of Cancer Therapy – Cognitive Function (FACT-Cog)  FACT-G = Functional Assessment of Cancer Therapy - General  PSQI = Pittsburgh Sleep Quality Index  Anx-Mood (Trait)= Beck Anxiety Inventory (BAI), Beck Depression Inventory-II (BDI-II),  Anx-Mood (State) = Positive and Negative Affect Schedule (PANAS), State-Trait Anxiety Inventory (STAI)  Pain (7 days) = Pain Intensity (7 days), the Promis Pain Interference CAT  Pain (Right now) = Pain Intensity (Right now)
														
	
* The PI will record all reportable events with start dates occurring any time after informed consent is obtained until 7 (for non-serious AEs) or 30 days (for SAEs) after Tc1.
														

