### 4.1 DESCRIPTION OF THE STUDY DESIGN

Tightly controlled experimental laboratory studies (e.g., clinical trials with randomization) using *Cannabis* products available in state-regulated markets are simply, at this point, not possible owing largely to federal law and the University requirements related to the Controlled Substances Act and Drug Free Schools and Communities Act. Because a traditional clinical trial design is not possible given the current federal status of *Cannabis* products, we will use a patient-oriented, prospective observational design. Specifically, individuals who have already decided to try *Cannabis* for their cancer treatment-related symptoms will initiate use of an orally administered product they have selected. A research assistant will provide information on the range of edible cannabis products and basic information about their various cannabinoid profiles, approximate prices, and nearby locations where participants may choose to purchase their product. The participants will then purchase the product and decide how often and how much to use. This approach is consistent with federal law and supported by our preliminary and ongoing studies (1R01AT009541-01, 1R01DA044131-01, CDPHE2902, R01DA039707). Participants will take the product as they see fit, without any frequency or dosing instructions from study staff, for two weeks, at which time they will be scheduled for their Pre- and Post- Administration Assessment (Ta1-Tc1) so that we may examine the acute effects of the product. The final follow-up will be one month later via an online survey sent directly to the participant via email. Details about the various study sessions are provided in Section 7.

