### **7 STUDY PROCEDURES AND SCHEDULE**

#### **7.1 STUDY PROCEDURES/EVALUATIONS**

The complete schedule of measures taken at each assessment are outlined in Table 7.1.

Table 7.1: Schedule of Locations and Assessments			
Timepoint	Measures	Location	Compensation
Baseline (T00)	Pain interference, pain intensity, anxiety symptoms, state and trait anxiety, sleep, quality of life, objective cognition, subjective cognition, demographics, alcohol and substance use history, cancer staging/treatment regimen (EMR)	At home (online)	\$60, 1.5 hours
Two weeks ad libitum use		At home	
Pre-acute Cannabis use (Ta1)	Pain interference, pain intensity, anxiety symptoms, state and trait anxiety, sleep, quality of life, objective cognition, subjective cognition, alcohol and substance use history (timeline follow-back).	At home (online)	
1 hour post-acute Cannabis use (Tb1)	Pain intensity, state anxiety, objective cognition	At home (online)	
2 hour post-acute Cannabis use (Tc1)	Pain intensity, state anxiety, objective cognition	At home (online)	\$100, 2.5 hours
One month follow-up (M1)	Pain interference, pain intensity, anxiety symptoms, state and trait anxiety, sleep, quality of life, subjective cognition, other substance use, Disease status/treatment regimen (EMR)	At home (online)	\$10, 20 minutes

NOTES: EMR=electronic medical record, total compensation possible for 4 hours, 20 minutes of assessment=\$170

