### 8.4 REPORTING PROCEDURES

#### 8.4.1 ADVERSE EVENT REPORTING

[figure not shown]
The study team will adhere to the protocol detailed in the figure below for reporting adverse events.

The study team will record all reportable events with start dates occurring any time after informed consent is obtained until seven days after the last day of study participation. All AEs will otherwise be followed to adequate resolution or stabilization.

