#### 8.4.2 SERIOUS ADVERSE EVENT REPORTING

Since the study procedures are not greater than minimal risk, SAEs are not expected. Should an SAE occur, the study team will adhere to the protocol detailed in the figure below for reporting serious adverse events.

The study team will record all reportable events with start dates occurring any time after informed consent is obtained until 30 days after the last day of study participation. All SAEs will otherwise be followed to adequate resolution or stabilization.

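### The Table 7.3 footnote and sections 8.4.1 and 8.4.2 close adverse event recording about 30 days apart for a participant who completes the study

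*Combined protocol and SAP*

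**What the plan says.** Three current passages set the period for recording reportable events. All three start it at informed consent.

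- Table 7.3, footnote: recording runs "until 7 (for non-serious AEs) or 30 days (for SAEs) after Tc1". Tc1 is the two-hour post-use assessment in the two-week session.
- Section 8.4.1, adverse events: recording runs "until seven days after the last day of study participation".
- Section 8.4.2, serious adverse events: recording runs "until 30 days after the last day of study participation".

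Tc1 is not the last scheduled assessment. Section 4.1 states: "The final follow-up will be one month later via an online survey sent directly to the participant via email". Section 7.3.4, whose heading is the final study visit, describes follow-up "using an online survey one month (+/- 7 days) later (M1"), with payment and the last medical record review. The M1 row of Table 7.3 carries a mark for AEs. Section 8.3 has the research assistant ask at each visit about AEs and SAEs that have occurred since the one before.

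**The concern.** The footnote and section 8.4 read as the same rule, with the same start and the same 7 and 30 days, but they count from different days. For a completer those days are about a month apart. Whether a non-serious event in most of that month is recordable therefore depends on which page the staff member reads.

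The footnote also fits poorly with its own table. Staff are to ask at M1 about the whole interval since the two-week session, yet under the footnote non-serious recording has closed one week into that interval. Section 7.3.4 leaves participants free in that month to stay on the product, change it or stop. Events in that month are therefore part of what a safety record of this study would be expected to hold.

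**Working it through.** The plan gives no figure for the length of either window in study days, so there is none to reproduce. The check is date arithmetic.

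**Inputs**
- Tc1: baseline + 14 days, +/- 4 days (section 7.3.3).
- M1: Tc1 + one month, +/- 7 days (section 7.3.4). The month is not given in days. I assume 30 and vary it from 28 to 31.
- Footnote end: Tc1 + 7 (non-serious), Tc1 + 30 (SAE).
- Section 8.4 end: last day of participation + 7 (AE), + 30 (SAE). I take that day as M1 for completers, which is an inference.

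**Date of M1**
M1 = Tc1 + 30, range Tc1 + 23 to Tc1 + 37.

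**Non-serious AEs**
- Footnote: Tc1 + 7.
- Section 8.4.1: Tc1 + 30 + 7 = Tc1 + 37 (23 + 7 = 30 to 37 + 7 = 44).
- Difference: 37 - 7 = 30 days (30 - 7 = 23 to 44 - 7 = 37).
- Footnote closure before M1: 30 - 7 = 23 days (23 - 7 = 16 to 37 - 7 = 30).

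**SAEs**
- Footnote: Tc1 + 30.
- Section 8.4.2: Tc1 + 30 + 30 = Tc1 + 60 (53 to 67).
- Difference: 60 - 30 = 30 days (23 to 37).
- Footnote closure relative to M1: 30 - 30 = 0 days nominally; 7 days after an early M1 (30 - 23) and 7 days before a late one (37 - 30).

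**Counted from baseline consent, with Tc1 at day 14 and M1 at day 44**

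| | Footnote | Section 8.4 |
|---|---|---|
| Non-serious AE | day 21 | day 51 (44 to 58) |
| SAE | day 44 | day 74 (67 to 81) |

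**Sensitivity**
- Moving Tc1 within its +/- 4 days shifts all the end dates together. The difference equals M1 minus Tc1, so it stays at 23 to 37 days.
- With a month of 28 to 31 days, the difference runs from 28 - 7 = 21 to 31 + 7 = 38 days. It is never zero.

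**Where the windows agree or fail**
They coincide only for someone whose last day of participation is the day of Tc1. For someone who leaves before Tc1, the footnote has no date to count from.

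**The case against.** The best defence is that the last day of participation is undefined and that section 7.3.4 calls the main observational portion complete after the two-week session. If participation ended there, the two windows would be the same. That M1 is the last day is indeed an inference, and this part of the objection stands. The Tc1 reading is much the weaker one, however. The same sentence of section 7.3.4 continues with follow-up to M1, section 4.1 calls M1 the final follow-up, and Table 7.3 schedules AEs there.

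The footnote might also be read as a baseline rule, because its asterisk appears in the baseline row. Its wording covers all start dates from consent onward, so that reading fails. The headings of Table 7.3 look shifted by a cell in the text available, but the AE mark at M1 holds under either alignment.

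A third argument is that little is at stake. Section 10.1 limits the endpoints to recruitment, section 8.4.2 describes the procedures as no more than minimal risk, and section 8.2.2 keeps expected events such as intoxication out of AE reporting under either window. The medical record review at M1 could also bring some events to light. All of this stands and limits the consequence, but it does not settle which events are recordable.

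A reader might go further and infer that nobody asks about AEs at M1. The two-week session states "A trained research assistant will meet remotely with the participant via phone or Zoom", whereas M1 is described as an emailed survey whose listed content (section 7.3.4 and Table 7.1) does not mention AEs. The documents do not support that conclusion. Section 8.3 requires the inquiry at each visit, Table 7.1 lists AEs at no time point, and the survey itself is not shown. Only the mode of contact is unstated.

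**Conclusion.** The inconsistency is real and lies between passages that are all in force. For completers the two recording windows end 30 days apart (23 to 37), assuming a 30-day month and M1 as the last day of participation. The footnote closes non-serious recording 23 days (16 to 30) before an AE assessment that the same table schedules, so following it would drop non-serious events that start from day 8 after Tc1. For SAEs the footnote reaches M1 nominally, and the shortfall falls mainly after it.

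The effect is on the completeness and consistency of the safety record. The recruitment endpoints and the sample size are untouched. The point is worth correcting, but its consequence is modest.

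Two stronger readings are not supported. One is that a known share of events would be lost: the differences are calendar days, and the documents give no event rate. The other is that section 5.4.2, which ends contact after withdrawal, contradicts section 8.4, which follows events to resolution. Following an event need not mean contacting the person, and the reporting figures are not shown.

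**What to change.** Reconcile the Table 7.3 footnote with sections 8.4.1 and 8.4.2 so that both places state one recording window for non-serious AEs and one for SAEs. Define the last day of study participation, including for someone who leaves before Tc1. Check that the agreed window is consistent with the AE inquiry already scheduled at M1 in Table 7.3 and section 8.3. As a side clarification, say how that inquiry is made at M1.

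The cost is a wording amendment with COMIRB approval (section 13.2), and possibly an AE item in the M1 survey or a short staff contact. The downside is that, if the window extends beyond M1, events in that final stretch would rest on passive capture, because no contact is scheduled then.

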## 8 ASSESSMENT OF SAFETY

### 8.1 SPECIFICATION OF SAFETY PARAMETERS

### 8.1.1 DEFINITION OF ADVERSE EVENTS (AE)

We define **adverse event** as “Any untoward or unfavorable medical occurrence in a participant, including any abnormal sign (e.g. abnormal physical exam or laboratory finding), symptom, or disease, temporally associated with the participants’ involvement in the research, whether or not considered related to participation in the research” ([http://www.colorado.edu/vcr/sites/default/files/IRB%20Policy%20Procedures-%20Final%2010-01-11\\_website.pdf](http://www.colorado.edu/vcr/sites/default/files/IRB%20Policy%20Procedures-%20Final%2010-01-11_website.pdf)).

### 8.1.2 DEFINITION OF SERIOUS ADVERSE EVENTS (SAE)

We define **serious adverse event** as an event that “Results in death, is life threatening, or places the participant at immediate risk of death from the event as it occurred, requires hospitalization, causes persistent or significant disability or incapacity, or is another condition which investigators judge to represent significant hazards.”

([http://www.colorado.edu/vcr/sites/default/files/IRB%20Policy%20Procedures-%20Final%2010-01-11\\_website.pdf](http://www.colorado.edu/vcr/sites/default/files/IRB%20Policy%20Procedures-%20Final%2010-01-11_website.pdf)).

### 8.1.3 DEFINITION OF UNANTICIPATED PROBLEMS (UAP)

This study will use the Office of Human Research Protection (OHRP) definition of an **unanticipated problem**: “involving risks to participants or others to include, in general, any incident, experience, or outcome that meets all of the following criteria:

- Unexpected in terms of nature, severity, or frequency given (a) the research procedures that are described in the protocol-related documents, such as the IRB-approved research protocol and informed consent document; and (b) the characteristics of the participant population being studied;
- Related or possibly related to participation in the research (“possibly related” means there is a reasonable possibility that the incident, experience, or outcome may have been caused by the procedures involved in the research); and
- Suggests that the research places participants or others at a greater risk of harm (including physical, psychological, economic, or social harm) than was previously known or recognized.”

## 8.2 CLASSIFICATION OF AN ADVERSE EVENT

### 8.2.1 SEVERITY OF EVENT

For AEs not included in the protocol-defined grading system, the following guidelines will be used to describe severity.

- **Mild** – Events require minimal or no treatment and do not interfere with the participant's daily activities.
- **Moderate** – Events result in a low level of inconvenience or concern with the therapeutic measures. Moderate events may cause some interference with functioning.
- **Severe** – Events interrupt a participant's usual daily activity and may require systemic drug therapy or other treatment. Severe events are usually potentially life-threatening or incapacitating.

### 8.2.2 EXPECTED ADVERSE EVENTS

Any medical condition that is present at the time that the participant is screened will be considered as baseline and not reported as an AE. Given the observational nature of our study and the disease state of our target participants, common events in our study population such as feeling intoxicated from marijuana, mild or consistent with baseline levels of pain, anxiety, drowsiness, or nausea are to be expected and will be documented on case report forms but not be reported as adverse events.

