**Objective and Subjective Cognitive Functioning.** The Telephone Interview for Cognitive Status (TICS) will be used at screening to assess for moderate to severe cognitive impairment that would preclude enrollment as a study participant. The TICS is a widely used and validated measure of cognitive impairment that is highly correlated to the Mini Mental State Exam (MMSE) . To assess objective cognitive functioning, we will conduct a neurocognitive battery on all participants that targets executive function. We will conduct this battery using Tatool, an open-source software developed to run psychological experimental studies. This battery includes tests for which deficits have been observed among cancer patients and include measures that are recommended by the International Cancer and Cognition Task Force. The battery covers the domains found to be sensitive to the effects of *Cannabis*. Specifically, the cognitive battery will include the Stroop Task to assess inhibition and the Shape/Color Shifting Task to assess shifting. We will assess subjective cognitive functioning with the Functional Assessment of Cancer Therapy – Cognitive Function (FACT-Cog), a reliable and valid assessment of perceived cognitive functioning specifically designed for cancer patients.

**Health/Disease Status and Treatment Regimen.** With the assistance of our oncology collaborators and OCRS staff, and with explicit informed consent from our patient participants, we will access Electronic Medical Records (EMRs) via the Health Data Compass coinciding with the Baseline encounter and the One Month Follow-up. We will obtain data regarding cancer staging, tumor characteristics, treatment regimen (observation versus chemotherapy, targeted therapy, immunotherapy, combination of therapies, or other), current medications and doses (including treatment-supporting medications only), and any co-existing conditions.

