### 8.3 TIME PERIOD AND FREQUENCY FOR EVENT ASSESSMENT AND FOLLOW-UP

The occurrence of an AE or SAE may come to the attention of study personnel during study sessions. All AEs including local and systemic reactions 1) not meeting the criteria for SAEs, 2) not included in the list of expected events in Section 8.2.3, or 3) beyond a threshold for an expected event listed in Section 8.2.3 (such as greater than mild symptoms or significant change from baseline in pain, anxiety, drowsiness, or nausea) will be captured on the appropriate case report form by a CUChange Lab professional research assistant. Information to be collected includes event description, time of onset, assessment of severity, and time of resolution/ stabilization of the event.

[figure not shown]
Changes in the severity of an AE will be documented to allow an assessment of the duration of the event at each level of severity to be performed. AEs characterized as intermittent require documentation of onset and duration of each episode.

At each study visit, the professional research assistant will inquire about the occurrence of AE/ SAEs since the last visit.

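### Section 8.2.2 has no exception for worsening, so on a literal reading non-serious deterioration of a pre-existing condition outside the listed expected events is left out of AE reporting

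*Combined protocol and SAP*

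**What the plan says.** Section 8.2.2 contains two separate exemptions.

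- **Conditions present at screening.** "Any medical condition that is present at the time that the participant is screened will be considered as baseline and not reported as an AE". No clause covers later worsening, and nothing asks for these conditions to be followed on a case report form.
- **Expected symptoms.** Intoxication is given as one example of an expected event, and the sentence continues: "mild or consistent with baseline levels of pain, anxiety, drowsiness, or nausea are to be expected and will be documented on case report forms". These events are kept out of AE reporting, but pain, anxiety, drowsiness and nausea are exempt only within a stated limit, and the events are still written down.

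Section 8.3 then describes which AEs are captured. One branch takes AEs that are not on the expected list. Another takes events "beyond a threshold for an expected event listed in Section 8.2.3", illustrated in brackets: "such as greater than mild symptoms or significant change from baseline in pain, anxiety, drowsiness, or nausea". Both branches refer to Section 8.2.3. In the text, 8.2.2 is followed directly by 8.3, and the expected events stand in 8.2.2.

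The general AE definition in 8.1.1 is broad. It applies "whether or not considered related to participation in the research" and does not mention pre-existing illness. The SAE definition in 8.1.2 rests on outcome ("Results in death, is life threatening, or places the participant at immediate risk of death from the event as it occurred, requires hospitalization", and further criteria) and has no exemption for pre-existing conditions.

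**The concern.** The participants have solid tumors, and some are on palliative treatment, so many can be expected to enter with existing complaints. In such people a harm from cannabis may well appear as worsening of something already there and not as a new diagnosis.

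The protocol itself points to the relevant areas. Section 2.1.3 lists insomnia among the most common complaints of cancer patients. Section 2.3.1 names acute mood shifts as a risk. Sections 2.1.2 and 2.1.4 treat cognitive effects as a central worry. None of these is among the four symptoms to which the 8.3 threshold is tied by example.

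If staff apply the first sentence of 8.2.2 as written, the AE record leans toward newly arising events. That record supports decisions elsewhere in the plan: an AE is a ground for ending participation (5.4.1), and unacceptable risk is a ground for suspending the study (5.5).

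**Working it through.** No arithmetic applies. The study has no hypothesis test, and Section 10.1 says its endpoints are recruitment based. The check is to follow different kinds of event through 8.1.2, 8.2.2 and 8.3 as written.

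| Event after consent | 8.2.2 | 8.3 or 8.1.2 | Result |
|---|---|---|---|
| New condition, absent at screening, not on the expected list | No exemption | 8.3, branch for AEs not on the list | Captured |
| Nausea, mild at baseline, becomes clearly worse | Falls outside the expected-symptom exemption | 8.3 threshold branch | Captured |
| Comorbidity present at screening, worsens to hospitalization | First sentence would exempt it from AE reporting | Meets the SAE definition | Captured as SAE |
| Depression, insomnia, mild cognitive impairment or comorbidity present at screening, worsens without meeting an SAE criterion | First sentence exempts it | Not a listed expected event, so the threshold branch does not reach it | Excluded on a literal reading |

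Three steps decide the last row.

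1. **The threshold branch.** It attaches to an expected event on the list. The bracketed examples illustrate thresholds for such events. They do not turn every condition present at screening into a listed event.
2. **The not-on-the-list branch.** This could seem to pick up worsened depression. But 8.3 opens by speaking of AEs, and 8.2.2 has already said that a condition present at screening is not reported as one. The branch helps only if the worsening is first accepted as an AE, which is the open question. The later sentence in 8.3 on documenting changes in severity has the same limit, because it concerns changes in an AE.
3. **Whether such participants can enrol.** Section 5.2 excludes moderate or severe impairment on the TICS, so milder impairment can enter. It excludes acute illness other than cancer that could affect cognition or compliance, so stable comorbidity can enter. Section 13.3 screens out psychological or cognitive problems that impede capacity, consent or participation, which is narrower than excluding everyone with low mood.

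The second row shows a further loose end. If the nausea is itself a condition present at screening, the first sentence of 8.2.2 exempts it while 8.3 captures it. The two sections are not reconciled, and the reference meant to link them points to a section that is not there. What counts as a significant change is not defined either.

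**The case against.** The strongest reply is that a baseline is a reference state. The second sentence of 8.2.2 uses the word in that sense, and 8.3 speaks of "significant change from baseline in pain, anxiety, drowsiness, or nausea". On that reading the state at screening is not an AE and a departure from it can be. The lists in both sections are introduced as examples and so are not closed. Staff ask about AEs and SAEs at every visit. The AE and SAE reporting figures in 8.4 are not shown and may hold more detail. This reading is reasonable, and it may be what the authors meant. But 8.2.2 does not say it, and a research assistant would have to choose it over the plain words.

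A second reply is that worsening would be seen anyway. Section 7.2.2 and Table 7.3 schedule mood, sleep and subjective cognition scales at baseline, two weeks and one month. The medical record is reviewed at baseline and one month for "current medications and doses (including treatment-supporting medications only), and any co-existing conditions". This stands as far as study data go. Nothing stated turns such a change into an AE.

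Two stronger readings should be set aside.

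- A reader might infer that deterioration of existing illness is never counted as a harm. The documents do not support that, because the SAE definition and the 8.3 threshold both catch part of it.
- A reader might infer that 8.2.2 flatly contradicts 8.1.1. The 8.1.1 definition requires a link in time with taking part, so leaving out a condition as it stood at screening is consistent with it. The tension arises only for later worsening, which can meet 8.1.1 yet is exempt under the literal 8.2.2. Relatedness is not the issue.

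**Conclusion.** The point holds in a limited form. As written, 8.2.2 removes conditions present at screening from AE reporting with no exception for worsening, and 8.3 restores only the listed expected events. What falls through on a literal reading is non-serious worsening of other pre-existing conditions.

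This is not confined to trivial events. Under 8.2.1 a severe event may interrupt usual activity and need systemic drug therapy, which does not by itself meet an SAE criterion. On the other hand, 8.2.1 also describes severe events as usually potentially life-threatening or incapacitating, so many of them would reach the SAE definition.

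The number of events affected cannot be given. The documents state neither how common co-existing conditions will be nor how often they will worsen. Section 10 plans no AE rate or comparison, and the recruitment endpoints do not depend on this rule. The consequence is therefore less complete safety data, with no effect on the primary result. The change is worth making because it corrects a stated rule at little cost. The conclusion assumes that staff follow the text as written and that the reporting figures not shown add no rule on worsening.

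**What to change.** 1. Add to 8.2.2 that a condition present at screening which increases in severity or frequency after informed consent is recorded as an AE, with onset at the date of worsening. Name the baseline medical record review and baseline questionnaires as the reference state.
2. In 8.3, extend the change-from-baseline threshold to all baseline conditions, and state what counts as a significant change.
3. Correct both references to 8.2.3 in 8.3 so that they point to 8.2.2.

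The cost is one sentence and two small edits. Co-existing conditions and questionnaire scores are already planned at baseline. One item needs checking first: the BDI-II appears in 7.2.2 and Table 7.3 but not in Tables 7.1 and 7.2, so its use as the reference for mood should be confirmed. Staff will record somewhat more AEs, and some will reflect disease progression. The 8.1.1 definition already accepts that, since it does not depend on relatedness.
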